4.4 MEASURES TO MINIMIZE/AVOID BIAS

4.4.1 RANDOMIZATION

This is a single-arm study and no randomization is applied.

4.4.2 BLINDING

This is an open-label study. No blinding is required.

4.5 DESCRIPTION OF THE INVESTIGATIONAL PRODUCT

4.5.1 INVESTIGATIONAL PRODUCT IDENTIFICATION

Drug name:	FIB Grifols 1.0 g powder and solvent for infusion
ATC code:	B02BB01.
Active principle:	Human fibrinogen 1.0 g/vial.
Pharmaceutic form:	Vials containing 1.0 g of FIB Grifols powder and vials containing 50 ml of sterile water as solvent for infusion.
Manufacturer and sponsor:	Instituto Grifols, S.A. [name]. Barcelona Spain

4.5.2 DOSAGE AND DOSAGE REGIMEN OF THE INVESTIGATIONAL PRODUCT

4.5.2.1 Dosage of investigational product

Dosage and regimen:	70 mg/kg body weight single dose
Administration via:	Intravenously
Administration form:	Investigational product will be prepared and administered as specified in the protocol Section 4.5.4

4.5.2.2 Dosage regimen of investigational product

A single infusion of fibrinogen concentrate at a dosage of 70 mg/kg body weight will be administered.

Only qualified health staff will administer the investigational product at the investigational site. Compliance with treatment will be recorded in the *Subject's Specific Administration Log* by the health staff.

During the treatment infusion, the subject's vital signs (temperature [T]; respiratory rate [RR]; heart rate [HR]; systolic blood pressure [SBP]; diastolic blood pressure [DBP]) will be monitored and recorded in the Day 0 Vital Signs worksheet as follows: 1) within 60

minutes before the beginning of the infusion; 2) at the beginning of the infusion, 3) every 20 ± 5 minutes during the infusion; 4) at the completion of the infusion and 5) within one hour after conclusion of the infusion.

The rate of infusion will be controlled by means of an infusion pump. The investigational medicinal product must be at room temperature and delivery will be performed at a constant rate not exceeding 5 mL/minute (it is acceptable to titrate up to this rate at the investigator's discretion). If an AE occurs during the infusion, the infusion rate may be reduced or the infusion may be interrupted until symptoms subside. Then, the infusion may be resumed up to a rate tolerated by the subject, but not exceeding 5 mL/minute.

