	
at 70 mg/kg body weight and will be followed for PK, efficacy, and safety assessments.
 
After the safety of fibrinogen concentrate FIB Grifols is assessed in at least 10 adult subjects and no safety issues are raised by the sponsor, the study will start to enroll approximately 10 pediatric subjects (<18 years) who will be dosed with study drug and followed for PK, efficacy, and safety assessments.
 
All enrolled subjects (both adult and pediatric) will have documented congenital fibrinogen deficiency manifested as afibrinogenemia but will not have received any fibrinogen-containing product therapy within the preceding 21 days before the infusion of study drug.
 
All subjects (both adult and pediatric) will be infused with the investigational product at 70 mg/kg body weight. PK parameters that will be calculated from plasma fibrinogen levels measured at different time points include: incremental in vivo recovery (IVR), area under the curve (AUC) calculated as AUC from zero to 14 days ($AUC_{0-14\text{days}}$) and AUC from zero to infinity ($AUC_{0-\infty}$), maximum plasma concentration (C_{\max}), time to the observed maximum plasma concentration (t_{\max}), half-life ($t_{1/2}$), mean residence time (MRT), volume of distribution (Vd), and clearance (Cl).
 
Hemostatic efficacy of the investigational product will be assessed by means of rotational thromboelastometry (ROTEM) measure of maximum clot firmness (MCF) at baseline and 1-hour post-infusion. Other thromboelastographic measures as well as standard coagulation tests will be also determined pre- and post-infusion.
 
Clinical safety, virus safety, and immunogenicity will be assessed in this clinical trial. Safety variables include adverse events (AEs), vital signs, physical assessments, laboratory tests, viral markers, and antibodies against human fibrinogen.
 
Allergic/hypersensitivity reactions and thrombotic events will be monitored during the study.
 
Stopping criteria have been established for immunogenic and thrombogenic events. Briefly, if a confirmed, single case of any of these events is reported after a subject has been dosed with study drug, any further enrollment and dosing of subjects in the study will be suspended until the event can be adequately assessed by the sponsor. The enrollment and dosing will only resume after explicit authorization by the sponsor.

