	
Markers of activation of coagulation (not applicable for pediatric subjects)
 
The following tests, indicative of activation of the coagulation: D-dimer, ATIII, thrombin-antithrombin III complex (TAT), and F₁₊₂ will be performed on frozen plasma samples taken at several time points throughout the study according to the schedule shown in Table 4-1 and Table 4-3 by the central laboratory of the study.
 
Immunogenicity (not applicable for pediatric subjects)
 
Serum/plasma samples taken only from adult subjects at several time points throughout the study according to the schedule shown in Table 4-1 and Table 4-3 will be analyzed for the generation of antibodies to fibrinogen by using a stepwise approach starting with a functional screening assay to detect neutralizing activity. In the event neutralizing activity is detected, samples will be further assessed by a confirmatory ELISA for the presence of antibodies to fibrinogen.
 
An additional aliquot of serum/plasma will be retained from all immunogenicity testing time points for re-testing if necessary.
 
Viral panel (not applicable for pediatric subjects)
 
Viral monitoring for each adult subject will be performed by means of serology and nucleic acid amplification technology (NAT) tests for following viruses: HAV, HBV, HCV, HIV-1 and HIV-2, and B19.
 
Serum/plasma samples from all subjects will be examined at baseline (prior to infusion on Day 0) and at different time points according to the schedule shown in Table 4-1, Table 4-2, and Table 4-3.
 
All serum/plasma samples will be sent to the central laboratory of the study for measurement of viral status. In case a subject is found to be positive for a particular virus at baseline, tests for this particular virus will not be performed at later time points during the study.
 
An additional aliquot of serum/plasma will be retained from all viral time points for re-testing if necessary.
 
Infusion and vital signs
 
During the treatment infusion, all subjects' vital signs (T, RR, HR, SBP, and DBP) will be monitored. Monitoring will be performed within 60 minutes before the beginning of the infusion, at the completion of the infusion, and within 30 minutes after conclusion of each infusion. During the infusion, vitals signs will be recorded every 20 ± 5 minutes.

--	---

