The following assessments and/or procedures will be carried out during infusion of the investigational medicinal product:

1. Vital signs: subject vital signs (T; RR; HR; SBP; DBP) will be monitored:
 - i. At the beginning of the infusion
 - ii. Every 20 ± 5 minutes during infusion
 - iii. At the completion of the infusion
2. Assessment of AEs: Any AE occurred during infusion will be recorded, including the infusion time elapsed and the infusion rate at the time of onset.

3. Assessment of concomitant medication: all medications other than investigational product administered to the subject during infusion will be recorded.

Infusion Visit (Day 0) – Post-Infusion

Blood samples taken on Infusion Visit (Day 0) Post-infusion period should be taken from the contralateral arm where the investigational medicinal product has been infused.

Infusion Visit (Day 0) – 30 Minutes Post-Infusion

The following assessments and/or procedures will be carried out 30 minutes after the completion of the infusion of the investigational medicinal product (\pm 5 minutes):

1. Fibrinogen levels (not applicable for pediatric subjects weighing <30 kg): plasma samples will be obtained for measurement of fibrinogen levels by two methods: fibrinogen activity (Clauss method), and fibrinogen antigen (ELISA).
Fibrinogen levels for PK calculations will be made by the central laboratory of the study.
2. Rotational thromboelastometry (not applicable for pediatric subjects): ROTEM will be performed on frozen plasma samples by the central laboratory and following parameters measured: CT, CFT, MCF, and α .
3. Standard coagulation tests (not applicable for pediatric subjects): following standard coagulation tests: TT, PT, and aPTT will be performed on frozen plasma samples at the central laboratory of the study.
4. Assessment of AEs: any new AE occurred will be recorded.
5. Assessment of concomitant medication: all new medications other than investigational product administered to the subject will be recorded.

Infusion Visit (Day 0) – 1 Hour Post-Infusion

The following assessments and/or procedures will be carried out one (1) hour after the end of infusion of the investigational medicinal product (\pm 10 minutes):

1. Vital signs: subject vital signs (T; RR; HR; SBP; DBP) will be monitored.
2. Fibrinogen levels: plasma samples will be obtained for measurement of fibrinogen levels by two methods: fibrinogen activity (Clauss method) and fibrinogen antigen (ELISA).

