8.2.4 LABORATORY PANELS

Laboratory tests will include:

1. Serum clinical chemistry: including creatinine, BUN, ALT, AST, ALP, LDH, TB, glucose, sodium, potassium, chloride and calcium.

2. Hematological parameters: CBC, including platelet count and differential leukocyte count.
3. Markers of activation of coagulation: different measures indicative of activation in the coagulation pathway (D-dimer, ATIII, TAT, F₁₊₂).

Blood specimens for laboratory tests will be collected at different time points throughout the study. Laboratory tests results will be collected in the corresponding CRF/eCRF entry. Abnormal (out of range) results will be flagged by the reporting laboratory. The investigator will be required to indicate the clinical relevance of out of range (abnormal) results. Laboratory results out of the normal range judged by the investigator as clinically relevant will be considered AEs.

In the case of markers of activation of coagulation, their relationship with plasma fibrinogen levels pre- and post-infusion will be studied.

In case of pediatric sampling, pediatric tubes would be provided to reduce the amount of blood drawn for lab works, including the complete elimination of virology, immunogenicity, and markers of activation of coagulation lab works. Pediatric subjects will not undergo Month 3 virology and immunogenicity follow-up visits, and their participation in the study will finish at the Week 4 Visit. Pediatric subjects weighing less than 30 kg will also have an even more reduced blood sampling schedule as detailed in [Table 4-4](#) and [Table 4-5](#):

- Day 0 - baseline (including the retention sample)
- Day 0 - 1 hour post-infusion
- Day 0 - 8 hours post-infusion
- Day 1 - 24 hours post-infusion
- Day 4 - 96 hours post-infusion
- Day 6 - 144 hours post-infusion and
- Day 9 - 216 hours post-infusion

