### 9.3 Descriptive Statistics of PK Parameters

Descriptive statistics (summarized separately for adult and pediatric populations, including n, mean, SD, 90% CI for mean, %CV, median, minimum, and maximum will be calculated for all PK parameters. Geometric mean and 90% CI for geometric mean will also be calculated for all PK parameters (except  $t_{max}$ ). If data allow, PK parameters for the pediatric population will also be summarized by age group as appropriate (e.g. <2,  $\geq 2$  - <12,  $\geq 12$  - <18 years).

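### In small children the plan permits an infusion with no vital-sign reading between its beginning and its completion; one early reading would close this minor gap cheaply.

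*Protocol*

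**What the plan says.** Section 4.5.2.2 of the protocol lists vital signs before the infusion, at its beginning, then "every 20 ± 5 minutes during the infusion; 4) at the completion of the infusion", and once more afterwards. Section 4.6.1.12 repeats the in-infusion readings, as does Section 4.6.2 ("Every 20 ± 5 minutes during infusion"). The Protocol Summary gives the same interval ("During the infusion, vitals signs will be recorded every 20 ± 5 minutes") but leaves out the reading at the beginning. Table 4-5 marks the same vital-sign cells for children on Day 0 as Table 4-3 does for adults.

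On rate, Section 4.5.2.2 says "delivery will be performed at a constant rate not exceeding 5 mL/minute", with titration up to that rate allowed. No limit per kg and no minimum duration is given. Section 4.5.4.2 advises a slow start with stepwise increases if tolerated, but names no starting rate or step. Sections 2.4, 4.5.4.2 and 6.1 all call for slow intravenous infusion.

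The protocol does adapt one procedure to body size, in Section 8.2.4: "Pediatric subjects weighing less than 30 kg will also have an even more reduced blood sampling schedule". That concerns blood draws only. Section 5.1 sets no lower age or weight limit. SAP Section 9.3 allows for very young children, if data permit: "PK parameters for the pediatric population will also be summarized by age group as appropriate (e.g. <2".

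**The concern.** Timed readings are spaced in minutes, while the length of the infusion scales with weight. In a light child the whole dose can therefore be in before the first timed reading falls due.

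This matters because the vital-sign route is one of the ways in which an infusion gets slowed. Under Section 8.2.2, a change from baseline of at least 30 bpm, 30 mm Hg or 1°C is reported as an adverse event. Section 8.3.6 counts such changes during the infusion as infusional events. Section 4.5.2.2 then provides: "If an AE occurs during the infusion, the infusion rate may be reduced or the infusion may be interrupted until symptoms subside". If the first reading after the beginning is the one at completion, a heart-rate, blood-pressure or temperature change without visible symptoms is found when no dose is left to slow.

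The adult stage does not test this situation. Children are enrolled only later ("After the safety of fibrinogen concentrate FIB Grifols is assessed in at least 10 adult subjects and no safety issues are raised"), but any subject above 35.7 kg has a timed reading inside the infusion at every permitted rate.

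**Working it through.** **Inputs.** Dose 70 mg/kg (Section 4.5.2.1); conversion 0.05 mL/mg (Section 4.5.4.1); vial 1 g in 50 mL (Section 4.5.3); ceiling 5 mL/min and first timed reading at 15 to 25 min (Section 4.5.2.2); mean infusion 1 h in adults and 0.5 h in children (SAP Section 4.1.1.1).

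**The plan's own figure.** 50 mL / 1000 mg = 0.05 mL/mg, which reproduces the stated conversion.

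**Shortest permitted infusion.** Volume = 70 × 0.05 = 3.5 mL/kg. Duration at the ceiling = 3.5 / 5 = 0.7 min/kg: 3.5 min at 5 kg, 7 min at 10 kg, 14 min at 20 kg, 21 min at 30 kg, 49 min at 70 kg.

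**Weight thresholds.** A ceiling-rate infusion lasts t minutes at weight 5t / 3.5. For t = 15 this is 75 / 3.5 = 21.4 kg; for t = 25 it is 125 / 3.5 = 35.7 kg.

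**How fast the infusion must run to miss the reading.** The infusion ends before minute t if its average rate exceeds 3.5w / t (w = weight in kg). Rates in mL/min, with percent of the ceiling:

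| Weight | First reading at 15 min | at 20 min | at 25 min |
|---|---|---|---|
| 5 kg | 1.17 (23%) | 0.88 (18%) | 0.70 (14%) |
| 10 kg | 2.33 (47%) | 1.75 (35%) | 1.40 (28%) |
| 20 kg | 4.67 (93%) | 3.50 (70%) | 2.80 (56%) |
| 30 kg | not possible | not possible | 4.20 (84%) |

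At 20 kg the 15-min reading is missed only close to the ceiling. At 10 kg or less a rate under half the ceiling is enough.

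**Effect of a slow start** (assumed: 5 min at 2 mL/min, then 5 mL/min). At 20 kg the infusion lasts 5 + (70 − 10) / 5 = 17 min, so a 15-min reading fits. At 10 kg it lasts 5 + (35 − 10) / 5 = 10 min, so none fits.

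**At the SAP mean of 30 min.** A 20 kg child runs at 70 / 30 = 2.33 mL/min and a 10 kg child at 35 / 30 = 1.17 mL/min. A timed reading at 15 to 25 min then has 50% to 17% of the dose still to come.

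**When an extra reading would have to be taken.** Assume that a set takes 2 to 5 min. At half volume it comes too late in the smallest children. At 5 kg and the ceiling, half volume is at 1.75 min, so even a 2-min set ends at 3.75 min, after the 3.5-min infusion. At 10 kg with the slow start above, half volume is at 5 + 7.5 / 5 = 6.5 min, and 79% to 100% of the dose is in when the set ends.

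At one quarter of the volume, with the start rate r held until the set is read, the fraction in at the end of a set lasting s minutes is 0.25 + r × s / (3.5w), capped at 100%:

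| Weight | r = 1 mL/min | r = 2 mL/min | r = 3 mL/min |
|---|---|---|---|
| 5 kg | 36% to 54% | 48% to 82% | 59% to 100% |
| 10 kg | 31% to 39% | 36% to 54% | 42% to 68% |
| 20 kg | 28% to 32% | 31% to 39% | 34% to 46% |

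Example at 20 kg and 2 mL/min: 0.25 + 4 / 70 = 31%; 0.25 + 10 / 70 = 39%.

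**The case against.** The strongest reply is that monitoring is not sparser in small children. Readings at the beginning and at completion are required, so an infusion shorter than 15 or 25 min leaves a gap shorter than 15 or 25 min, within what adults are allowed. This stands in full. A reader might infer from the thresholds that small children are observed less often; the documents do not support that. Only the timing of the reading relative to the remaining dose is at issue.

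A second reply is that short infusions are unlikely. Slow infusion is directed in three sections, the SAP's pediatric mean is 0.5 h, and the 35.7 kg figure combines the maximum rate with the latest permitted reading. This also stands, and it lowers the weight of the point. It does not remove it: slow is not given a number, and a mean does not exclude shorter individual infusions.

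A third reply is that staff can act without a timed reading. Section 4.5.4.2 says that the rate should come down, or the infusion be stopped for a time, if adverse events or intolerance occur. Section 4.6.1.14 requires watching for allergic signs, and extra readings are not barred. That is right. What remains is a measurable change without visible symptoms.

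Finally, the SAP's under-2 group is a conditional reporting category. It shows that such children are possible, not that a child of 5 or 10 kg was expected.

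**Conclusion.** The point holds as a minor safety improvement. The plan permits an infusion with no reading between beginning and completion below 21.4 kg, or below 35.7 kg if the first timed reading is at 25 min. The thresholds assume the ceiling rate throughout; at slower average rates they fall in proportion, for example to 10.7 and 17.9 kg at 2.5 mL/min.

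Three stronger readings are tempting and should be resisted. The documents show no individual short infusion, so it cannot be said that any child went without a reading. This is not a case of children being dosed before adult safety is known, since an adult safety review comes first. And no PK, efficacy or safety analysis is altered.

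The size of the benefit rests on assumptions that the documents do not settle: the starting rate (1 to 3 mL/min shown) and the time to take one set (2 to 5 min).

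**What to change.** Add to the Protocol Summary (infusion and vital signs) and to Sections 4.5.2.2, 4.6.1.12 and 4.6.2:

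> If the planned volume is under 125 mL (body weight under about 36 kg), start at a slow rate as advised in Section 4.5.4.2, take one set of vital signs when about one quarter of the planned volume has been infused, and do not increase the rate until that set has been read.

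A stated starting rate, lower for the lightest children, would strengthen the rule, because the 5 kg result depends most on it.

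**Cost.** One extra vital-sign set, one worksheet line and some added infusion time per small child. Each minute at 2 instead of 5 mL/min adds 1 − 2/5 = 0.6 min. Against running at the ceiling throughout, that is 0.6 × (4.4 + 2 to 5) = about 4 to 6 min at 10 kg, 0.6 × (8.75 + 2 to 5) = about 6 to 8 min at 20 kg, and 0.6 × (15.3 + 2 to 5) = about 10 to 12 min at 35 kg. Part of this is already implied by the advised slow start. Dose, ceiling and blood sampling do not change, and no pause is planned.

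**Alternative.** A 30-min minimum duration (at most 3.5 / 30 = 0.117 mL/kg/min, binding below 150 / 3.5 = 42.9 kg) would secure a timed reading with 17% to 50% of the dose left. It changes the rate rule itself and is the larger amendment.

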4.5.3 PACKAGING AND LABELLING OF THE INVESTIGATIONAL PRODUCT

FIB Grifols will be supplied in type II glass vials containing 1 g of human fibrinogen (powder for infusion) and a vial containing 50 mL of water for injection (solvent).

Packaging and labeling of FIB Grifols supplies will comply with local regulatory requirements and will be translated into local languages when required per local regulations.

IMPORTANT:

INVESTIGATIONAL PRODUCT PACKAGINGS SHOULD BE STORED FOR ACCOUNTABILITY RECONCILIATION BY THE CLINICAL MONITOR BEFORE BEING DESTROYED.

4.5.4 STORAGE, PREPARATION, DISPENSATION AND ADMINISTRATION OF THE INVESTIGATIONAL PRODUCT

Instituto Grifols, S.A. will supply vials for intravenous administration of investigational product (FIB Grifols).

A drug repository company may be contracted for drug distribution to investigational sites where applicable. Investigational product will be maintained within respective recommended temperature conditions.

4.5.4.1 Storage and preparation of the investigational product

FIB Grifols must be stored between 2°C and 25°C and must not be frozen. Moreover, FIB Grifols must be kept in a secure room with access restricted to necessary study site personnel.

The pharmacist must keep the investigational product accountability by means of the *Investigational Site Specific Drug Accountability Log*.

FIB Grifols solution preparation:

FIB Grifols solution will be prepared at investigational site pharmacy by the pharmacist responsible of the investigational product or by qualified personnel delegated, as indicated in the Human Plasma-derived Intravenous Fibrinogen Grifols Investigator's Brochure [1].

The product should be administered intravenously within 12 hours after reconstitution with the solvent supplied. Meanwhile, it should be stored between 2°C and 25°C, for a maximum time of 12 hours.

Total dose or volume of the investigational product to be administered will be calculated according to the following formula:

$$\text{Total dose (mg)} = \text{Body weight (kg)} \times 70 \text{ mg/kg}$$

$$\text{Approximate total volume (mL)} = \text{Total dose (mg)} \times 0.05 \text{ mL/mg}$$

IMPORTANT:

INVESTIGATIONAL PRODUCT PACKAGINGS SHOULD BE STORED FOR ACCOUNTABILITY RECONCILIATION BY THE CLINICAL MONITOR BEFORE BEING DESTROYED.

4.5.4.2 Dispensation and administration of the investigational product

Investigational product dispensation:

The pharmacist or the delegated qualified person is responsible for preparing the investigational product and must complete a dispensation register (*Subject Specific Dispensing Log*). The investigational product will be delivered to the staff performing the infusion.

Investigational product administration:

Qualified health staff will administer the investigational product, keeping maximum asepsis, at the investigational site. These qualified health staff must also complete an administration register in order to check treatment compliance (*Subject's Specific Administration Log*).

The investigational medicinal product to be administered must be at room temperature before administration and the administration should be performed by slow intravenous infusion at an infusion rate not exceeding 5 mL/minute. It is advisable to start the infusion with a slow rate and, if well-tolerated by the subject, then to incrementally increase it.

If the administration is problematic (ie, AEs or intolerance occurs), the rate of administration should be reduced, and even temporarily stopped until symptoms subside. In case of an anaphylactic shock, the administration of the product must be immediately discontinued, and the hospitals/centers current specific guidelines for shock therapy should be followed.

4.6 EXPECTED DURATION OF SUBJECT'S PARTICIPATION AND DESCRIPTION OF THE SEQUENCE AND DURATION OF THE TRIAL PERIOD

The total estimated maximum duration of subject's participation could be approximately 3 months and 3 weeks for adult subjects, starting with the Screening Visit (within 21 days

before Day 0). After infusion of the investigational product on Day 0, the PK, efficacy, and clinical safety evaluation period (Day 0 to Day 14) will commence. The subjects will be followed up for up to 3 months for safety, virology, and immunogenicity assessments. Pediatric subjects will not undergo Month 3 assessments and their study participation will conclude after the Week 4 Visit.

Clinical trial consists of:

1. Screening Visit: up to 21 days before the infusion visit (Day 0)
2. Infusion Visit: administration of the investigational medicinal product on Day 0
3. PK, Efficacy, and Clinical Safety Evaluation Visits: Day 0 to Day 14
4. Follow-Up Period up to 3 months: including safety follow-up visits (virology and immunogenicity assessments) on Day 21 ± 1 day, Week 4 ± 3 days
5. Month 3 ± 7 days (adult subjects only)

Clinical trial finalization will coincide with the last visit of the last subject included in the study.

Schedules of procedures for adult subjects are provided in [Table 4-1](#), [Table 4-2](#), and [Table 4-3](#). Schedules of procedures for pediatric subjects are provided in [Table 4-4](#) and [Table 4-5](#).

Table 4-1 Schedule of Procedures of the Study in Adult Subjects

Procedures and assessments	Visits	Screening Visit (up to 21 days prior to infusion visit)	Infusion Visit*	Pharmacokinetic, Efficacy, and Clinical Safety Evaluation Visits							Safety, Virology, and Immunogenicity Follow-Up Visits		
				Day 0	Day 1	Day 2	Day 4	Day 6	Day 9	Day 14	Day 21 ± 1 Day	Week 4 ± 3 Days	Month 3 ± 7 Days
Informed Consent		X											
HIPAA ¹		X											
Demographics ²		X											
Medical History		X											
Height and Weight			X										
Inclusion/Exclusion Criteria		X	X										
Physical Assessment		X	X	X								X	
Medications ³		X	X	X	X	X	X	X	X	X	X	X	X
Pregnancy Test ⁴			X ^B										
Serum Clinical Chemistry ⁵			X ^B	X				X		X			
Hematology ⁶			X	X				X		X			
Fibrinogen Levels (Clauss and Antigen)		X ^A	X ^{B,C}	X ^C	X ^C	X ^C	X ^C	X ^C	X ^C				
Rotational Thromboelastometry ⁷				X	X	X	X	X	X				
Standard Coagulation Tests ⁸				X	X	X	X	X	X				
Markers of Activation of Coagulation ⁹				X	X	X	X	X	X				
Immunogenicity Testing ¹⁰					X						X		X
Viral Panel ¹¹				X						X	X	X	X
Vital Signs ¹²				X	X			X		X			
Adverse Events		X	X	X	X	X	X	X	X	X	X	X	X
Thrombotic Events Risk Assessment (including Wells Score)			X	X	X	X	X	X	X	X	X	X	X
Allergic/hypersensitivity Reactions				X	X	X	X	X	X	X	X	X	
Risk Assessment													
Retention Sample ¹³			X						X	X	X	X	X

* See specific Day 0 flowchart for adult subjects (Table 4-3)

1. Health Information and Accountability Act authorization form (if applicable).
2. Date of birth, gender, and ethnic origin.
3. Prior medications for the last 3 months (Screening Visit only) and concomitant medications.
4. Human chorionic gonadotropin-based blood or urine assay for women of childbearing potential.
5. Creatinine, blood urea nitrogen (BUN), total bilirubin (TB), alkaline phosphatase (ALP), alanine aminotransferase (ALT), aspartate aminotransferase (AST), lactate dehydrogenase (LDH), glucose, sodium, potassium, chloride, and calcium.
6. Red blood cells (RBC) count, hemoglobin (Hgb), hematocrit (Hct), mean corpuscular hemoglobin (MCH), mean corpuscular hemoglobin concentration (MCHC), mean corpuscular volume (MCV), white blood cell (WBC) count and differential, and platelet count.
7. Thromboelastographic parameters: clotting time (CT), clot formation time (CFT), maximum clot firmness (MCF), and alpha angle (α).
8. Thrombin time (TT), prothrombin time (PT), and activated partial thromboplastin time (aPTT).
9. D-dimer, antithrombin III (ATIII), thrombin-antithrombin III complex (TAT), prothrombin fragments F_{1+2} (F_{1+2})
10. Antibodies to fibrinogen. Day 0 sample to be collected pre-infusion. For details, see specific Day 0 flowchart for adult subjects ([Table 4-3](#)).
11. Serology and nucleic acid amplification technology (NAT) testing for virus safety. For details, see the corresponding Schedule for Virology Testing ([Table 4-2](#)).
12. Heart rate (HR), respiration rate (RR), systolic and diastolic blood pressure (SBP and DBP), and temperature (T).
13. A serum/plasma retention sample will be kept frozen at -70°C.

^ASites that cannot perform fibrinogen levels determinations (by both Clauss and antigen method) locally will have a blood sample taken at Screening Visit 14 days prior to Baseline Visit and have it analyzed for this parameter by both methods at the central laboratory of the study for verification of the eligibility against the Inclusion/Exclusion criteria. In these cases, the sample for assessing the Inclusion/Exclusion criteria will not be taken at Baseline Visit. Samples for pharmacokinetic (PK) will still be taken at Baseline Visit.

^BBaseline pregnancy test (when applicable), serum clinical chemistry and fibrinogen levels (when applicable) results from samples drawn within 24 hours prior to the scheduled infusion and tested locally must be available prior to infusion for verification of the eligibility against the Inclusion/Exclusion criteria.

^CBaseline (and subsequent) fibrinogen levels for PK calculations (Clauss and antigen methods [ELISA]) will be measured at the central laboratory of the study.

Table 4-2 Schedule for Virology Testing (Adult Subjects Only)

Visits	Viral Panel											
	Day 0 Baseline (within 60 min prior to the infusion)		Day 9 ^A		Day 14 ^A		Day 21 ± 1 Day ^A		Week 4 ± 3 Days ^A		Month 3 ± 7 Days ^A	
	Serology	NAT*	Serology	NAT	Serology	NAT	Serology	NAT	Serology	NAT	Serology	NAT
Viruses												
Hepatitis A Virus (HAV)	X ¹ (IgM&IgG)	X ¹				X	X (IgM&IgG)	X	X (IgM&IgG)	X		
Hepatitis B Virus (HBV)	X ^{1,2}	X ¹				X		X	X ⁴	X	X ⁴	
Hepatitis C Virus (HCV)	X ¹	X ¹								X	X ⁵	X
Human Immunodeficiency Viruses, types 1 and 2 (HIV-1/2)	X ¹	X ^{1,3}								X ³	X ⁶	X ³
Parvovirus B19	X ¹ (IgM&IgG)	X ¹	X (IgM&IgG)	X	X (IgM&IgG)	X						

1. Sample will be always analyzed.

2. Total anti-HBc (IgM & IgG)

3. NAT for HIV-1 only

4. HBsAg

5. In case of HCV positive antibody screen, a recombinant immunoblot assay will be performed.

6. In case of HIV positive antibody screen, a Western blot assay for HIV-1 will be performed.

^A Samples would be analyzed for a particular virus only in the event of negative results of analysis of NAT, IgM, and IgG for that particular virus performed on all previous samples.

* NAT = Nucleic acid amplification technology

Table 4-3 Schedule of Procedures During Day 0 (Infusion Visit) in Adult Subjects

Procedures and assessments	Visits	Baseline (prior to infusion)	During infusion	After Infusion				
				30 minutes	1 hour	2 hours	4 hours	8 hours
Inclusion/Exclusion Criteria		X						
Height and weight		X						
Physical Assessment		X						X
Medications ¹		X	X	X	X	X	X	X
Pregnancy Test ²		X ^A						
Serum Clinical Chemistry ³		X ^A						
Hematology ⁴		X						
Fibrinogen Levels (Clauss and Antigen)		X ^{A,B}		X	X	X	X	X
Rotational Thromboelastometry ⁵		X		X	X		X	
Standard Coagulation Tests ⁶		X		X	X		X	
Markers of Activation of Coagulation ⁷		X			X		X	
Immunogenicity Testing		X						
Viral Panel ⁸		X						
Vital Signs ⁹		X	X		X			
Adverse Events		X	X	X	X	X	X	X
Thrombotic Events Risk Assessment		X			X		X	
Allergic/hypersensitivity Reactions Risk Assessment		X			X		X	
Retention Sample ¹⁰		X			X		X	
Footnotes continued on next page								

1. Concomitant medications.
2. Human chorionic gonadotropin (HCG)-based blood or urine assay for women of childbearing potential.
3. Creatinine, blood urea nitrogen (BUN), total bilirubin (TB), alkaline phosphatase (ALP), alanine aminotransferase (ALT), aspartate aminotransferase (AST), lactate dehydrogenase (LDH), glucose, sodium, potassium, chloride, and calcium.
4. Red blood cells (RBC) count, hemoglobin (Hgb), hematocrit (Hct), mean corpuscular hemoglobin (MCH), mean corpuscular hemoglobin concentration (MCHC), mean corpuscular volume (MCV), white blood cell (WBC) count and differential and platelet count.
5. Thromboelastographic parameters: clotting time (CT), clot formation time (CFT), maximum clot firmness (MCF), and alpha angle (α)
6. Thrombin time (TT), prothrombin time (PT) and activated partial thromboplastin time (aPTT).
7. D-dimer, antithrombin III (ATIII), thrombin-antithrombin III complex (TAT), prothrombin fragments F_{1+2} (F_{1+2})
8. Serology and nucleic acid amplification technology (NAT) testing for virus safety. For details, see the corresponding Schedule for Virology Testing ([Table 4-2](#)).
9. Heart rate (HR), respiration rate (RR), systolic and diastolic blood pressure (SBP and DBP), and temperature (T).
10. A serum/plasma retention sample will be kept frozen at -70°C.

^A The results from baseline pregnancy test (when applicable), serum clinical chemistry and fibrinogen levels (when applicable) from samples drawn within 24 hours prior to the scheduled infusion and tested locally must be available prior to infusion for verification of the eligibility against the Inclusion/Exclusion criteria. In case fibrinogen levels determination for verification of the Inclusion/Exclusion criteria is performed at the Screening Visit, this sample will not be taken at Baseline Visit. Sample for PK will still be taken at Baseline Visit.

^B Baseline fibrinogen levels for PK calculations (Clauss and antigen methods [ELISA]) will be measured at the central laboratory of the study.

Table 4-4 Schedule of Procedures of the Study in Pediatric Subjects

Procedures and assessments	Visits	Screening Visit (up to 21 days prior to infusion visit)	Infusion Visit*	Pharmacokinetic, Efficacy, and Clinical Safety Evaluation Visits						Safety Follow-Up Visits ¹¹		
				Day 0	Day 1	Day 2	Day 4	Day 6	Day 9	Day 14	Day 21 ± 1 Day	Week 4 ± 3 Days
Informed Consent		X										
HIPAA ¹		X										
Demographics ²		X										
Medical History		X										
Height and Weight			X									
Inclusion/Exclusion Criteria		X	X									
Physical Assessment		X	X	X								X
Medications ³		X	X	X	X	X	X	X	X	X		X
Pregnancy Test ⁴			X ^B									
Serum Clinical Chemistry ⁵			X ^B	X				X		X		
Hematology ⁶				X	X			X		X		
Fibrinogen Levels (Clauss and Antigen)	X ^A	X ^{B,C}	X ^C	X ^{C,12}	X ^C	X ^C	X ^C	X ^C	X ^{C,12}			
Rotational Thromboelastometry ⁷			X									
Standard Coagulation Tests ⁸			X									
Vital Signs ⁹			X	X				X		X		
Adverse Events	X	X	X	X	X	X	X	X	X	X		X
Thrombotic Events Risk Assessment (including Wells Score)			X	X	X	X	X	X	X	X		X
Allergic/hypersensitivity Reactions Risk Assessment			X	X	X	X	X	X	X	X		X
Retention Sample ¹⁰		X										

- See specific Day 0 flowchart for pediatric subjects (Table 4-5).

1. Health Information and Accountability Act (HIPAA) authorization form (if applicable).
2. Date of birth, gender, and ethnic origin.
3. Prior medications for the last 3 months (Screening Visit only) and concomitant medications.
4. Human chorionic gonadotropin (HCG)-based blood or urine assay for females of childbearing potential.
5. Creatinine, blood urea nitrogen (BUN), total bilirubin (TB), alkaline phosphatase (ALP), alanine aminotransferase (ALT), aspartate aminotransferase (AST), lactate dehydrogenase (LDH), glucose, sodium, potassium, chloride, and calcium.
6. Red blood cells (RBC) count, hemoglobin (Hgb), hematocrit (Hct), mean corpuscular hemoglobin (MCH), mean corpuscular hemoglobin concentration (MCHC), mean corpuscular volume (MCV), white blood cell (WBC) count and differential, and platelet count.
7. Thromboelastographic parameters: clotting time (CT), clot formation time (CFT), maximum clot firmness (MCF), and alpha angle (α).
8. Thrombin time (TT), prothrombin time (PT), and activated partial thromboplastin time (aPTT).
9. Heart rate (HR), respiration rate (RR), systolic and diastolic blood pressure (SBP and DBP), and temperature (T).
10. A serum/plasma retention sample will be kept frozen at -70°C.
11. Pediatric subjects will not undergo Month 3 virology and immunogenicity follow-up visits.
12. Not applicable for pediatric subjects weighing <30 kg.

^ASites that cannot perform fibrinogen levels determinations (by both Clauss and antigen method) locally will have a blood sample taken at Screening Visit 14 days prior to Baseline Visit and have it analyzed for this parameter by both methods at the central laboratory of the study for verification of the eligibility against the Inclusion/Exclusion criteria. In these cases, the sample for assessing the Inclusion/Exclusion criteria will not be taken at Baseline Visit. Samples for pharmacokinetic (PK) will still be taken at Baseline Visit.

^BBaseline pregnancy test (when applicable), serum clinical chemistry and fibrinogen levels (when applicable) results from samples drawn within 24 hours prior to the scheduled infusion and tested locally must be available prior to infusion for verification of the eligibility against the Inclusion/Exclusion criteria.

^CBaseline (and subsequent) fibrinogen levels for PK calculations (Clauss and antigen methods [ELISA]) will be measured at the central laboratory of the study.

Table 4-5 Schedule of Procedures During Day 0 (Infusion Visit) in Pediatric Subjects

Procedures and assessments	Visits	Baseline (prior to infusion)	During infusion	After Infusion				
				30 minutes	1 hour	2 hours	4 hours	8 hours
Inclusion/Exclusion Criteria		X						
Height and Weight		X						
Physical Assessment		X						X
Medications ¹		X	X	X	X	X	X	X
Pregnancy Test ²		X ^A						
Serum Clinical Chemistry ³		X ^A						
Hematology ⁴		X						
Fibrinogen Levels (Clauss and Antigen)		X ^{A,B}		X ⁹	X	X ⁹	X ⁹	X
Rotational Thromboelastometry ⁵		X			X			
Standard Coagulation Tests ⁶		X			X			
Vital Signs ⁷		X	X		X			
Adverse Events		X	X	X	X	X	X	X
Thrombotic Events Risk Assessment		X			X		X	
Allergic/hypersensitivity Reactions Risk Assessment		X			X		X	
Retention Sample ⁸		X						
Footnotes continued on next page								

1. Concomitant medications.
2. Human chorionic gonadotropin (HCG)-based blood or urine assay for females of childbearing potential.
3. Creatinine, blood urea nitrogen (BUN), total bilirubin (TB), alkaline phosphatase (ALP), alanine aminotransferase (ALT), aspartate aminotransferase (AST), lactate dehydrogenase (LDH), glucose, sodium, potassium, chloride, and calcium.
4. Red blood cells (RBC) count, hemoglobin (Hgb), hematocrit (Hct), mean corpuscular hemoglobin (MCH), mean corpuscular hemoglobin concentration (MCHC), mean corpuscular volume (MCV), white blood cell (WBC) count and differential and platelet count.
5. Thromboelastographic parameters: clotting time (CT), clot formation time (CFT), maximum clot firmness (MCF), and alpha angle (α).
6. Thrombin time (TT), prothrombin time (PT) and activated partial thromboplastin time (aPTT).
7. Heart rate (HR), respiration rate (RR), systolic and diastolic blood pressure (SBP and DBP), and temperature (T).
8. A serum/plasma retention sample will be kept frozen at -70°C.
9. Not applicable for pediatric subjects weighing <30 kg.

